6.3 ANALYSIS OF THE SECONDARY EFFICACY ENDPOINT(S)

6.3.1 Vaccine Series Initiation

For the secondary efficacy measure, we will test the following null hypothesis:

H₀: Vaccination series initiation rate among children of caregivers assigned to the Vaccine Uptake app will not differ from the vaccine series initiation rate among children of caregivers assigned to the General Health app

vs

H₁: Unvaccinated children of caregivers assigned to the Vaccine Uptake app will be more likely to achieve COVID-19 vaccine series initiation than those children whose caregivers are assigned to the General Health app

For each vaccine-eligible child, this secondary endpoint will be defined as whether or not the child initiates the COVID-19 vaccine series during the 16 weeks of study participation. Vaccine series initiation will be receipt of at least 1 valid dose of any COVID-19 vaccine product. Vaccine doses for series initiation will only be valid for study purposes if given within the 16 weeks of study participation.

Univariate Analysis

The secondary vaccine series initiation endpoint will be collected as a dichotomous variable (yes/no). We will report the probability of COVID-19 vaccine series initiation for each intervention group (Vaccine Uptake app vs General Health app). Initially, an unadjusted non-modeling approach using SAS PROC FREQ will be used estimate the relative risk (RR) for COVID-19 vaccine series initiation (with Wald 95% CI), with the General Health app intervention group as the reference group. The analysis will be performed for all three populations (ITT, mITT, and PP).

Secondary and Multivariable Analysis

A mixed-effect Poisson regression with robust error variance will be used to report adjusted relative risk (RR) with 95% CI accounting for site random effect and controlling for clustering by caregiver. The multivariable model will allow adjustment for covariates. The analysis will be performed for all three populations (ITT, mITT, and PP).

6.3.2 Parental Attitude Toward Pediatric COVID-19 Vaccination

The study team will evaluate parental attitude toward pediatric COVID-19 vaccination by using the modified SAGE Vaccine Hesitancy Scale that includes ten statements with ordinal responses using a 5-point Likert scale. At baseline and week 16, the study statisticians will generate summary statistics and graphical display for each of the 10 questions for the two intervention groups.

Analysis for SAGE Vaccine Hesitancy Scale Items

For each item, the study statisticians will report response frequency overall and by intervention groups. A mean score chi-square test (i.e., test of location shift) will be used to examine the association between responses and intervention groups. For the adjusted analysis, a linear mixed model will be used to account for parent/caregivers nested within clinics and allow adjustment for covariates. The analysis will be performed for all three populations (ITT, mITT, and PP).

Analysis for SAGE Vaccine Hesitancy Scale Composite

A composite vaccine hesitancy score will be the sum of the 10 items/statements after reverse coding items 1, 2, 3, 4, 6, 7, and 8 (range of 10 to 50). The study statisticians will provide summary statistics including means and standard deviation at baseline and week 16. A linear mixed model will be used to account for parent/caregivers nested within clinics and allow adjustment for covariates. The analysis team will report point estimates for the intervention group mean difference along with 95% CI. The analysis will be performed for all three populations (ITT, mITT, and PP).

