#### **11.4.3 ANALYSIS OF THE SECONDARY ENDPOINT(S)**

**Vaccine Series Initiation.** For each vaccine-eligible child, this secondary endpoint will be defined as whether or not the child initiates the COVID-19 vaccine series during the 16 weeks of study participation. Vaccine series initiation will be receipt of at least 1 valid dose of any COVID-19 vaccine product. Vaccine doses for series initiation will only be valid for study purposes if given within the 16 weeks of study participation. The statistical team will use a mixed model with the binomial distribution and the logit link to compare the two intervention groups with respect to the proportions of children who initiate COVID-19 vaccination, using site as a random effect and controlling for clustering by caregiver.

**Parental attitude toward pediatric COVID-19 vaccination.** The study team will evaluate parental attitude toward pediatric COVID-19 vaccination by using the vaccine hesitancy questionnaire that includes ten statements with ordinal responses using a 5-point Likert scale. At baseline and week 16, the study statisticians will generate summary statistics for each of the 10 questions for the two intervention groups. Similarly, the change in responses from baseline to end of study will be determined for each intervention group. The study statisticians will use the general linear mixed model to evaluate the intervention effect on responses to each measure at baseline and end of study, and they will use this model to evaluate the change in each measure by using site as a random effect. Within each intervention arm and for each statement, the study statisticians will use the Wilcoxon signed rank test to determine if the change in response from baseline to end of study is significantly different from zero.

---

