4.1 SECONDARY ENDPOINTS

1. Proportion of children who receive ≥ 1 dose of the COVID-19 vaccination series, as verified in state, clinic, or participant-held records

Def: Initiation of the COVID-19 vaccination series will be coded as 1=Yes or 0 = No. Verification of vaccine receipt will occur by any of the following methods:

- Photograph of the child's vaccine card, furnished by the caregiver
- Medical records documentation of child vaccine receipt
- Recorded vaccine receipt in the appropriate state vaccine registry

2. Change in enrolled parent/caregiver domain scores from baseline to week 16 on the modified SAGE Vaccine Hesitancy Scale adapted for the COVID-19 Vaccine

Def: The modified SAGE Vaccine Hesitancy Scale includes ten statements with ordinal responses using a 5-point Liker scale (1 = Strongly Disagree; 2 = Somewhat Disagree; 3 = Neutral; 4 = Somewhat Agree; 5 = Strongly Agree). A composite vaccine hesitancy score will be the sum of the 10 items/statements after reverse coding items 1, 2, 3, 4, 6, 7, and 8 (range of 10 to 50). The reverse coding makes directionality uniform across the ten items so that a higher composite score indicates more hesitancy.¹⁰ Additionally, each statement/item will be treated as an individual outcome measure of hesitancy (range of 1 to 5).

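### SAP 6.3.2 leaves open whether endpoint 2 is analysed as week 16 or as change and names no baseline covariate; week 16 adjusted for baseline should be prespecified, with its limits stated

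*SAP*

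**What the plan says.** SAP 4.1 (Secondary Endpoints) defines the endpoint as "Change in enrolled parent/caregiver domain scores from baseline to week 16 on the modified SAGE Vaccine Hesitancy Scale adapted for the COVID-19 Vaccine". It then describes a composite of 10 to 50 and ten item scores of 1 to 5.

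SAP 6.3.2 gives the analysis. For the composite, "The study statisticians will provide summary statistics including means and standard deviation at baseline and week 16". For the adjusted item analysis, and in the same terms for the composite, "a linear mixed model will be used to account for parent/caregivers nested within clinics and allow adjustment for covariates". For the composite, "The analysis team will report point estimates for the intervention group mean difference along with 95% CI". The unadjusted item test reads: "A mean score chi-square test (i.e., test of location shift) will be used to examine the association between responses and intervention groups". None of these sentences names the response variable, the visit, a change score or a baseline term, and the section contains no list of covariates.

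Protocol 11.4.3 is more explicit about change. After the summaries at each visit it says: "Similarly, the change in responses from baseline to end of study will be determined for each intervention group". It then applies a general linear mixed model, and "they will use this model to evaluate the change in each measure by using site as a random effect". It names no baseline covariate either, and it covers the ten statements but not the composite.

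On timing, Protocol 8.3 and SAP 3.2.1 place randomization before the baseline assessment. Protocol 7.5.3 sends the baseline survey link after app registration. SAP 3.2.2 plans no masking. Protocol Table 1 schedules the hesitancy items at baseline and week 16 only.

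**The concern.** The wording of SAP 6.3.2 fits at least three analyses: week 16 alone, the change score, and week 16 adjusted for baseline. If the baseline score is free of any app effect, all three estimate the same difference between arms, so validity is not at stake. They differ in standard error and in how they treat chance imbalance at baseline. Week 16 alone leaves the imbalance in the estimate, and a change score over-corrects for it whenever r is below 1.

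In an unmasked trial that choice should be fixed before results are seen. Protocol 11.4.1 leaves the detailed analytical plan to the SAP, and on this endpoint the SAP is less specific than the protocol. At stake are the precision of a named secondary endpoint and a clear statement of what its mean difference is a difference of.

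**Working it through.** **The plan's own figure.** The documents give no standard deviation, correlation, effect size or power for endpoint 2. The only sample size is for the primary endpoint (SAP 3.3), and it reproduces. With 30% against 40%, two-sided 0.05 and 90% power, (1.960 + 1.282)² × (0.21 + 0.24) / 0.10² = 472.8 children per arm. Multiplying by the design effect 1 + (2 − 1) × 0.60 = 1.6 and dividing by 2 children per caregiver gives 378.3, so 379 caregivers per arm, 758 in total. 758 / 0.85 = 892. Below, 379 per arm serves only as an illustrative number of respondents.

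**Precision.** Assume equal variances at both visits, complete data and correlation r. The range of r is an assumption. Relative to the unadjusted week-16 comparison, the variance of the arm difference is 2(1 − r) for raw change and 1 − r² for week 16 adjusted for baseline. The ratio of adjusted to change is (1 − r²) / [2(1 − r)] = (1 + r)/2.

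| r | Week 16 only | Raw change | Adjusted | Adjusted ÷ change |
|---|---|---|---|---|
| 0.3 | 1 | 1.40 | 0.91 | 0.65 |
| 0.4 | 1 | 1.20 | 0.84 | 0.70 |
| 0.5 | 1 | 1.00 | 0.75 | 0.75 |
| 0.6 | 1 | 0.80 | 0.64 | 0.80 |
| 0.7 | 1 | 0.60 | 0.51 | 0.85 |
| 0.8 | 1 | 0.40 | 0.36 | 0.90 |

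Both 1 − r² and (1 + r)/2 are at most 1, so under these assumptions the adjusted analysis is never less precise than either alternative.

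In detectable differences at 379 per arm and 80% power, ignoring clinic, week 16 alone gives (1.960 + 0.842) × √(2/379) = 0.204 SD. Multiplying by √(1 − r²) gives 0.194, 0.176 and 0.145 SD for the adjusted analysis at r = 0.3, 0.5 and 0.7. Multiplying by √[2(1 − r)] gives 0.241, 0.204 and 0.158 SD for change.

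**A baseline measured after app registration.** Suppose a fraction f of the week-16 effect is already in the baseline score. With equal variances the regression slope on baseline is r, so the adjusted analysis recovers 1 − r·f of the effect. Change recovers 1 − f, and week 16 alone recovers all of it.

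| f | Adjusted, r = 0.5 | Adjusted, r = 0.7 | Change |
|---|---|---|---|
| 0.10 | 0.95 | 0.93 | 0.90 |
| 0.25 | 0.875 | 0.825 | 0.75 |

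A simulation of 400,000 caregivers agrees within its error (0.885 and 0.814 at f = 0.25).

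Against week 16 alone, the adjusted analysis still has the better ratio of effect to standard error while 1 − r·f > √(1 − r²), that is f < [1 − √(1 − r²)]/r. The limit is 0.15 at r = 0.3, 0.27 at r = 0.5, 0.41 at r = 0.7 and 0.50 at r = 0.8.

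**Missing baselines.** In a complete-case model with a fraction m of baselines missing, the relative variance is (1 − r²)/(1 − m). At an assumed m = 0.10 this is 0.75/0.90 = 0.83 for r = 0.5, so the 25% cut falls to 17%. For r = 0.3 it is 0.91/0.90 = 1.01, so the 9% cut becomes a 1% loss.

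**The case against.** The strongest reply is that SAP 6.3.2 is under-specified rather than wrong. That stands. A reader might infer that the section discards the baseline score, leaving only a week-16 comparison or a pooled two-visit model that ignores correlation within caregiver. The documents do not support this. The endpoint is defined as change, Protocol 11.4.3 models change, and the SAP models allow unnamed covariates, which does not exclude baseline. A mixed model of the change score is the most natural reading. It is still not the adjusted analysis, and permission to adjust is not a prespecified covariate.

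A reader might also infer a variance cut of a quarter or more. No r is given. Against week 16 alone a quarter needs r of at least 0.5. Against change it needs r of at most 0.5. The two conditions meet only at r = 0.5.

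Nor is adjustment free. The baseline survey comes after randomization and app registration in an unmasked trial, so adjustment can attenuate the effect, and a complete-case model loses caregivers with no baseline. Both points stand. The attenuation is nevertheless smaller than for the change score that the endpoint definition already implies.

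Finally, the unadjusted item test is a valid randomized comparison and is already paired with an adjusted model, so it need not be removed.

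**Conclusion.** The concern holds as a gap in specification with a better method available. The endpoint is change from baseline to week 16, SAP 6.3.2 fixes neither the response nor a baseline covariate, and Protocol 11.4.3 models raw change. For assumed r between 0.3 and 0.8, adjustment brings the variance to 0.91 to 0.36 of a week-16-only analysis and 0.65 to 0.90 of a change analysis, given equal variances and complete data.

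The gain over week 16 alone is small at low r, and missing baselines or early app effects can cancel it. How large f and m will be cannot be known from the documents. This is a should-fix matter for a secondary endpoint and leaves the primary analysis untouched.

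**What to change.** In SAP 6.3.2:

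1. State that the main analysis of the composite, and the adjusted model for each item, regresses the week-16 score on arm and baseline score with clinic in the model, and reports the baseline-adjusted mean difference with its 95% CI. The mean-score test for items may stay as a supporting analysis.
2. Keep caregivers with a missing baseline, for example through a likelihood-based model of both visits with a common baseline mean across arms, or a simple baseline imputation.
3. Add two sensitivity analyses: the week-16 comparison without baseline, and a repeat excluding caregivers with an app session before the baseline survey. The time stamps in Protocol 7.5.2 make the second feasible. Say that this exclusion selects on a post-randomization event that may differ by arm, so it is supportive only.
4. Give any expected precision gain as 1 − r² over a stated range of r.

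Reconcile Protocol 11.4.3 with this: the response, the baseline covariate, the composite, clinic against site, and week 16 in place of end of study, since Table 1 collects hesitancy only at baseline and week 16.

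The cost is a few sentences in the SAP, a matching protocol clarification and some programming. The scores and time stamps are already planned.

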6.4 ANALYSIS OF SAFETY ENDPOINTS

Because this study is of an educational intervention and poses minimal risk, adverse events (AEs) and serious adverse events (SAEs) are not expected. The study team will not solicit AEs or SAEs but will provide all participants with a site-specific telephone number to report AEs/SAEs. The study team will track severe and serious AEs that are potentially study related.

All AEs recorded during the study period will be coded with Medical Dictionary for Regulatory Activities (MedDRA) Version March 2018. Summaries of AE will be tabulated for the following types:

- Numbers (%) of participants with any AE
- Numbers (%) of participants with any SAE
- Numbers (%) of participants withdrawn from intervention due to AE

All reported AEs will be assigned the system organ class and preferred term according to MedDRA. Listing of all AEs will be tabulated by intervention group and by system organ class and preferred term.

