### 10.3.4 TIME PERIOD AND FREQUENCY FOR EVENT ASSESSMENT AND FOLLOW-UP

The study team will provide participants with a site-specific telephone number to report severe AEs or SAEs. Since this study will not administer the COVID-19 vaccine or any other intervention beyond the app, the study

**Title:** Improving pediatric COVID-19 vaccine uptake using an mHealth tool: a randomized, controlled trial

**PI:** [name]

---

team will not actively solicit AEs or SAEs or monitor any events related to COVID-19 vaccination. When site coordinators or site investigators learn of a severe AE or SAE, they will refer participants to their primary care physician and will record the severe AE or SAE into the EDC and will track the SAE.

Site coordinators/research team members will record severe AEs as described in the next section and in the (MOP). Severe AE data collection typically includes event description, time of onset, if available, resolution time and day, if available, and the site investigator's assessment of severity, relationship to study participation or intervention (assessed only by those with the training and authority to make a diagnosis), and time of resolution/stabilization of the event. Site coordinators/research team members must appropriately document severe AEs occurring during the trial, regardless of relationship to the trial. The study team will track severe AEs until one of the following criteria are met: resolution, the condition stabilizes, the event is otherwise explained or is judged by the site investigator to be no longer clinically significant, or the participant withdraws from the study. The study team will track all SAEs by asking site coordinators/research team members about the SAE every 14 days until resolution or until the site investigator determines the event is chronic or until the participant is stable. The DCOC may request other supporting documentation of the event, and site investigators or site coordinators should provide this documentation as soon as possible.

Site coordinators/research team members will document changes in a severe AE in the source document and EDC to allow for an assessment of the duration of the event. Severe AEs characterized as intermittent require documentation of onset and duration of each episode.

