Appendix

Appendix A	Modified SAGE Vaccine Hesitancy Scale	14
------------	---	----

LIST OF ABBREVIATIONS

ACIP	Advisory Committee on Immunization Practices
AE	Adverse Event
CDC	Centers for Disease Control
CI	Confidence Interval
COVID-19	Coronavirus Disease 2019
ECHO	Environmental Influences on Child Health Outcomes
ICH	International Conference on Harmonization
ITT	Intent-to-Treat
ISPCTN	IDeA States Pediatric Clinical Trials Network
MedDRA	Medical Dictionary for Regulatory Activities
mHealth	Mobile Health
MITT	Modified Intent-to-Treat
PP	Per Protocol
SAE	Serious Adverse Event
SAP	Statistical Analysis Plan
SAS	Statistical Analysis System
SD	Standard Deviation
UAMS	University of Arkansas for Medical Sciences

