1. PURPOSE OF THE STATISTICAL ANALYSIS PLAN

The statistical analysis plan (SAP) is a document intended to provide a detailed and comprehensive layout of the planned analytical methodology to be used for the multi-center randomized study of a vaccine communication mHealth app on parental decisions to vaccinate their children against coronavirus disease 2019 (COVID-19) of UAMS Protocol 273761, Improving Pediatric COVID-19 Vaccine Uptake Using an mHealth Tool: A Randomized, Controlled Trial. This SAP applies to the protocol Version 09 dated on December 16, 2022. The purpose of this plan is to provide general, and in some instances, specific guidelines from which the analysis will proceed.

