5. STATISTICAL PRINCIPALS

5.1 GENERAL APPROACH

The statistical team will conduct all statistical analyses following the statistical principles for clinical trials as specified in ICH Statistical Principles for Clinical Trials (ICH Topic E9). The study team will describe and justify any deviations from the planned analyses in the final integrated clinical study report. The study team will present all study data and summary tables for the overall study and by study sites.

The statistical team will summarize descriptive statistics for continuous data by using mean and standard deviation or median and interquartile range, as appropriate. The team will also summarize categorical data by using frequency and percent.

The statistical software package SAS Version 9.4 or higher (SAS Institute, Cary, NC, USA) or STATA version 14 or higher (Stata Statistical Software, College Station, TX: StatCorp LLC) will be used to perform all analyses and to summarize data.

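### The SAP pins adverse-event coding to a March 2018 MedDRA version, so a recorded COVID-19 illness in a caregiver could not be identified by preferred term in the by-arm listing

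*SAP*

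**What the plan says.** SAP 6.4 sets the coding rule in one sentence: "All AEs recorded during the study period will be coded with Medical Dictionary for Regulatory Activities (MedDRA) Version March 2018". It then requires coding at two levels, "All reported AEs will be assigned the system organ class and preferred term according to MedDRA", and a display by arm at those levels: "Listing of all AEs will be tabulated by intervention group and by system organ class and preferred term". It also plans three counts of participants: those with any AE, those with any SAE, and those withdrawn from the intervention because of an AE.

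The dictionary is identified by month and year only. There is no version number and no provision for a later release. SAP 5.1 words its software versions differently: "The statistical software package SAS Version 9.4 or higher", with the same open wording for the alternative package.

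On which events are recorded, Protocol 10.3.4 says that site staff "must appropriately document severe AEs occurring during the trial, regardless of relationship to the trial". Protocol 10.3.2 makes inpatient hospitalization a criterion of seriousness.

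**The concern.** The SAP's list of abbreviations gives the disease its full name, "Coronavirus Disease 2019". A dictionary issued in March 2018 is older than the disease, so it cannot contain a term specific to it. If a caregiver has a severe or serious COVID-19 illness during the trial and the site learns of it, the SAP as written leaves the coder only a more general term.

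The preferred-term listing is the one planned display that would tell a reader what the events were. In a trial about COVID-19 vaccination, COVID-19 illness is a natural thing to look for there, and the listing could not show it under its own name.

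**Working it through.** The plan gives no figure to reproduce. The check compares dates and then follows an event through the recording rules.

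**Dates**
- Dictionary: March 2018 (SAP 6.4).
- Disease: not before January 2019, from its name in the documents. Even the end of March 2018 is 9 months earlier (April to December 2018).
- Protocol to which the SAP is tied: "This SAP applies to the protocol Version 09 dated on December 16, 2022". From March 2018 to December 2022 is 4 × 12 + 9 = 57 months.

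The named dictionary therefore predates the disease by at least 9 months and the cited protocol version by about 57 months. This needs no knowledge of what MedDRA contains; the order of the dates is enough.

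**Can such an event reach the listing?**
1. *Whose event?* The protocol's definitions make the parent or caregiver the participant; the child takes part only through record review. The event must be the caregiver's own.
2. *Is it recorded?* Under Protocol 10.3.4, severe AEs are documented whatever their cause. A caregiver hospitalized with COVID-19 meets the SAE definition in 10.3.2. The site must first hear of it, because AEs are not solicited (Protocol 10.2, SAP 6.4).
3. *Is it coded?* SAP 6.4 applies coding to all recorded AEs, so yes, with the March 2018 dictionary.
4. *Is it listed?* SAP 6.4 lists all AEs by arm, system organ class and preferred term, so yes, but under a term that is not specific to COVID-19.

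**What depends on the preferred term?**
- The listing by arm: yes.
- The three participant counts in SAP 6.4: no. An event counts once whatever term it carries.
- Series completion, series initiation and the hesitancy scale: no.
- Sample size, power and error rate: no.

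**Where the scope is stated differently**
- Protocol 10.3.4: severe AEs documented regardless of relationship.
- Protocol 10.2 and the opening of SAP 6.4: severe and serious events are tracked if potentially related to the study.
- Protocol 11.4.4: the summary by arm covers intervention-related severe AEs and SAEs.
- Rest of SAP 6.4: all recorded AEs are coded and listed.

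Under the narrower statements, a COVID-19 illness judged unrelated might not be tabulated at all. Under the wider ones, it is tabulated with a non-specific term.

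**The case against.** The strongest reply is that this is a dated phrase with almost nothing behind it. AEs and SAEs are not expected, and the potential events named in Protocol 10.3.3.3 are anxiety, depression and feeling stigmatized or threatened, none of them specific to a 2019 disease. A caregiver's COVID-19 illness is hardly attributable to an information app, so under Protocol 11.4.4 it might never enter a table by arm. The event description stays in the data capture system (Protocol 10.3.4), so coding does not erase it. COVID-19 status and history are also collected by survey at baseline and week 16 (Protocol 7.5.3, Table 1). Protocol 12.1.8.1 leaves coding dictionaries to a data management plan, which is not among the documents and may name another version.

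Most of this stands, and it limits the point to one listing. It does not remove it. SAP 6.4 still says that all recorded AEs are coded with this dictionary and listed. If the data management plan names another version, the two documents conflict, which is a further reason to correct the SAP.

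A reader might infer three stronger things that the documents do not support:
- *That multisystem inflammatory syndrome in children and vaccine reactions would also be miscoded.* The child is not the participant, and Protocol 10.3.4 says events related to COVID-19 vaccination are not monitored.
- *That the safety comparison between arms is distorted.* The number of affected events is unknown and may be zero. No test, stopping rule or endpoint uses the listing, and nothing in the documents ties a caregiver's own COVID-19 illness to the assigned app. The arms are not cleanly opposed on vaccination either: Protocol 8.1.2 describes the control app's notifications as also prompting vaccination of the child.
- *That COVID-19 events would be scattered over several terms.* That depends on dictionary content that the documents do not give.

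**Conclusion.** The point holds as a minor error in a stated rule. As written, SAP 6.4 requires a dictionary that cannot hold a preferred term for COVID-19, so any recorded COVID-19 illness in a caregiver would be unidentifiable by preferred term in the listing by arm. Its reach is that listing alone, and probably few or no events; the documents give no expected number. Participant counts and all efficacy results are unaffected.

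This rests on two assumptions: that the stated month and year denote the release to be used, and that the wide recording scope of Protocol 10.3.4 governs what enters the SAP tables. If the narrower scope governs, even fewer events are affected, but the version should still be corrected.

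**What to change.** In SAP 6.4, replace the March 2018 reference with a MedDRA version identified by number and current at the time of coding or at database lock. Either convention works if it is stated. Give the version in the report, make it agree with the data management plan named in Protocol 12.1.8.1, and recode any events already coded.

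In the same revision, reconcile the scope of recorded and tabulated AEs across Protocol 10.2, 10.3.4 and 11.4.4 and SAP 6.4, so that it is clear whether unrelated severe events appear in the tables by arm.

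The version change is one phrase plus recoding of what is probably a handful of events at most. The scope change is a sentence or two. Neither touches the design, the endpoints or the sample size.
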